**7.3.3.7. Visit 13 - Safety Follow-Up and Step 5 Pre-Dose Safety Assessment**

Occurs between 7 and 14 days after Visit 12 and within 21 days of Step 5, Visit 14.

The pre-dose safety labs must be reviewed and signed off by the study PI or designee prior to Visit 14. If the participant does not meet one or more of the requirements of the pre-dose safety lab assessments, repeat of the abnormal lab/s can occur one time only.

After repeat testing, any lab values that remain outside the guidelines listed below but are considered clinically non-significant and documented as such by the study PI (or designee), may proceed to the dosing/infusion visit after review and approval of the case by the protocol and/or safety committee.

Please reference the SOE for clinical and research procedures done at this visit.

Hematology	Laboratory Value
ANC	$\geq 1,500 / \text{mcL}$
Platelets	$\geq 125,000 / \text{mcL}$
Hemoglobin	$\geq 12 \text{ g/dL}$ (male) and $\geq 11.0 \text{ g/dL}$ (females)
Chemistry	
K + levels	WNL
Mg ++ levels	WNL
Glucose	$\leq$ Grade 1 (fasting or non- fasting)
Renal	
Creatinine	$< 1.3 \times \text{ULN}$
Hepatic	
Total bilirubin	$< 1.6$ times the ULN range. If total bilirubin is elevated, direct bilirubin must be $< 2$ times the ULN range.
AST (SGOT) and ALT (SGPT)	$\leq 2.5 \times \text{ULN}$
Alkaline Phosphatase	$\leq 2.5 \times \text{ULN}$
Other Testing	
Serum pregnancy test (all females)	Negative
RPR	No active infection
HIV RNA	$< 50$ copies

CD4	$\geq 350$
-----	------------

Estimated Blood Volume: up to 60 mL

Participants will be given 1 dose of VOR 400 mg to take home. Upon verification of acceptable labs, participants will be contacted to verify date and time of Visit 14 and also to verify the time participant is to take the 11th dose of VOR that morning. Plans will be made for participants to return the dose of VOR 400 mg to the study coordinator should the participant fail to have acceptable pre-dose labs for Step 5.

The study coordinator and the participant will discuss Step 5 visit schedule and VOR dosing schedule. Participant will be given a VOR dosing schedule/calendar illustrating the 72-hour dosing schedule (inclusive of date and time) and the dates of the HXTC infusions. Participants will be provided with information about VOR as well as information regarding the storage and handling of VOR at home. All of this information will be reviewed prior to sending participant home with the 11th VOR dose.

#### 7.3.4. Step 5 (Visits 14 – 20) Second Series of VOR 400 mg x 10 doses and three HXTC Infusions

Participants with acceptable pre-dose safety labs as determined in Visit 13 are eligible to start dosing with VOR and receive their 3rd HXTC infusion in Step 5, Visit 14.

#### Visit Windows for Step 5

Visit #	Visit Evaluations	Visit Window
Visit 14	VOR Dose #11 and HXTC Infusion #3	$\leq 21$ days after Visit 13
Visit 15	Safety check and Research Labs	1 - 3 days after Visit 14
	VOR Dose #12	3 days after Visit 14 (Dose 11 + 3 days)
	VOR Dose #13	6 days after Visit 14 (Dose 11 + 6 days)
	VOR Dose #14	9 days after Visit 14 (Dose 11 + 9 days)
	VOR Dose #15	12 days after Visit 14 (Dose 11 + 12 days)
Visit 16	VOR Dose #16 and HXTC Infusion #4	15 days after Visit 14 (Dose 11 + 15 days)
Visit 17	Safety Check and Research Lab	1 - 3 days after Visit 16
	VOR Dose #17	3 days after Visit 16 (Dose 11 + 18 days)
	VOR Dose #18	6 days after Visit 16 (Dose 11 + 21 days)
	VOR Dose #19	9 days after Visit 16 (Dose 11 + 24 days)
Visit 18	VOR Dose #20	12 days after Visit 16 (Dose 11 + 27 days)
Visit 19	HXTC Infusion #5	1-3 days after Visit 18
Visit 20	Safety Check and Research Lab	1-3 days after Visit 19

#### 7.3.4.1. Visit 14 – 1st Visit of 2nd series

All female participants will be required to have a negative POC urine pregnancy test within 48 hours of Visit 14. If, despite the documentation of infertility, a female participant has a positive pregnancy test at this visit, she will be discontinued from the study and not receive any additional VOR doses or HXTC infusions.

Estimated Blood Volume: up to 25 mL

##### 7.3.4.1.1. VORINOSTAT 400 mg

Participants take one dose of VOR 400 mg PO the morning of this visit and document the time of the dose. This is the first dose (Dose #11) in the 2nd series of 10 doses.

Reference section 7.3.3.1.1 for dosing time and process prior to infusion.

##### 7.3.4.1.2. Pre - 3rd HXTC Infusion

The participant will come to the clinic approximately 3.5 - 4 hours after taking their VOR dose for pre-infusion evaluations.

Reference section 7.3.3.1.2. and SOE for visit procedures and processes.

Documented PI review of clinical labs from Visit 13 as well as review of clinical assessments done at this visit are required prior to the thawing and infusion of HXTC study product.

Note: Administration of HXTC can be delayed up to 1 week pending resolution of physical findings or lab abnormalities.

##### 7.3.4.1.3. Administration of HXTC

Reference section 7.3.3.1.3 for infusion guidelines.

##### 7.3.4.1.4. Post Infusion

Provide participant with doses #12 – #16 of VOR 400 mg to take home.

The study coordinator will contact participants via their preferred way of communication approximately 2 to 3 days after study product administration to inquire about any reactions or potential TEAEs. Instruct the participant to contact the study coordinator or investigator if such any adverse events occur after this infusion or at any point during the study. The study coordinator can combine this assessment with VOR dosing reminder when these events overlap.

7.3.4.2. **Visit 15 – Safety Follow-Up Visit**

The study participant will have a post HXTC infusion follow-up visit per SOE with labs drawn 1 – 3 days post infusion.

Estimated Blood Volume: up to 55 mL

7.3.4.3. **Visit 16 - Dose #6 of VOR and 4th HXTC Infusion**

All female participants require a negative POC urine pregnancy test within 48 hours of infusion visit. If, despite the documentation of infertility, a female participant has a positive pregnancy test at this visit, they will be discontinued from the study and not receive the HXTC infusion or additional doses of VOR.

Estimated Total Blood Volume: up to 45 mL

7.3.4.3.1. **VORINOSTAT 400 mg**

Participants take VOR 400 mg PO the morning of this visit and document the time. This is the 6th dose in the series of 10 doses.

Reference section 7.3.3.1.1. for dosing time and process prior to infusion.

7.3.4.3.2. **Pre – HXTC Infusion**

Safety evaluations and research lab collection:

- Collect safety labs (STAT) or within 48 hours of the visit.
- Collect research labs on the day of visit only.
  - Collect approximately 4 hours after AM VOR dose. Collection can be +/- one hour of the 4-hour time point.

Documented PI review of clinical labs as well as review of clinical assessments done at this visit are required prior to the thawing and infusion of HXTC study product.

Administration of HXTC can be delayed up to 1 week, pending resolution of physical findings or lab abnormalities.

**7.3.4.3.3. Administration of HXTC Therapy**

Reference section 7.3.3.1.3 for infusion guidelines.

**7.3.4.3.4. Post Infusion**

Provide participant with the last four (4) doses of VOR 400 mg to take home.

The study coordinator will contact participants via their preferred way of communication approximately 2 to 3 days after study product administration to inquire about any reactions or potential TEAEs. Instruct the participant to contact the study coordinator or investigator if any adverse events occur after this infusion or at any point during the study. Study coordinator can combine this assessment with VOR dosing reminder when these events overlap.

**7.3.4.4. Visit 17 – Safety follow-up**

The study participant will have a post HXTC infusion follow-up visit per SOE with labs drawn 1 – 3 days post infusion.

Estimated Total Blood Volume: up to 25 mL

**7.3.4.5. Visit 18 – Last dose of VOR 400mg - Dose #20 )**

Participants take their last dose (Dose #20) of VOR 400 mg PO in the morning and document the time of the dose. Participants will come to research clinic approximately 4 – 6 hours after this dose.

Clinical assessments and sample collections will be performed per SOE.

Estimated Blood Volume: up to 35 mL

**7.3.4.6. Visit 19 – 5th and final HXTC Infusion**

All female participants require a negative POC urine pregnancy test within 48 hours of infusion visit. If, despite the documentation of infertility, a female participant has a positive pregnancy test at this visit, they will be

discontinued from the study and not receive the HXTc infusion or additional doses of VOR.

Estimated Blood Volume: up to 25 mL

#### 7.3.4.6.1. Pre – HXTc Infusion

Reference section 7.3.3.1.2. and SOE for visit procedures and processes.

Safety evaluations and research lab collection:

- Collect safety labs (STAT) or within 48 hours of the visit.
- Collect research labs on the day of visit only.

Documented PI review of clinical labs as well as review of clinical assessments done at Visit 18 as well clinical assessments from this visit are required prior to the thawing and infusion of HXTc study product.

Administration of HXTc can be delayed up to 1 week, pending resolution of physical findings or lab abnormalities.

#### 7.3.4.6.2. Administration of HXTc Infusion

Please reference section 7.3.3.1.3. for infusion guidelines.

#### 7.3.4.6.3. Post Infusion

The study coordinator will contact participants via their preferred way of communication approximately 2 to 3 days after this visit to inquire about any reactions or potential TEAEs. Instruct the participant to contact the study coordinator or investigator if any such adverse events occur after this infusion or at any point during the study.

#### 7.3.4.7. Visit 20 - Safety Follow-up

The study participant will have a follow-up visit per SOE with labs drawn 1 – 3 days post infusion.

Estimated Total Blood Volume: up to 25 mL

### 7.3.5. **Step 6 (Visits 21, 23 and 24) Immune Monitoring Follow-up**

These last three visits (Visits 21, 23 and 24) are longitudinal follow-up to evaluate for a sustained immune response. There is a leukapheresis at Visit 23 to measure the effect on the frequency of resting cell infection by QVOA.

**NOTE: THE PROTOCOL AMENDMENT FOR VERSION 4.0 DATED 31 JANUARY 2022 ELIMINATED STEP 6 VISITS 22, 25, AND 26 OF THE PROTOCOL.**

7.3.5.1. **Visit 21**

The clinical and research assessments and procedures occur per SOE at Visit 21.

Estimated Blood Volume: up to 50 mL

7.3.5.2. **Visit 23 and End of Study Intervention Visit**

The clinical and research assessments and procedures occur per SOE at Visit 23.

A leukapheresis is performed at this visit.

Estimated Total Blood Volume: up to 70 mL

7.3.5.3. **Visit 24**

In addition to the participants completing all study visits, participants terminated, at any time point after initiating Step 4, will complete this visit after completing Visit 23.

The clinical and research assessments and procedures occur per SOE at Visits 24.

Estimated Blood Volume: up to 55mL

Visit 24 will be the last study visit and the end of study.

**7.4. Screening Failure and Re-screening Procedures**

Participants unable to meet laboratory values as defined in the protocol and defined inclusion/exclusion criteria may repeat the disqualifying lab/s once to meet eligibility prior to enrolling at Visit 2.

Participants unable to meet protocol defined eligibility criteria at the Screening Visit after repeating disqualifying labs per protocol, can re-screen again at the Principal

Investigator's (or designee) discretion. In such cases, the participant keeps the same PID.

**7.4.1. Failure of the frequency of resting CD4+ T cell infection to be  $\geq 0.3$  infected cells per million as determined by QVOA assay at baseline evaluation.**

If a participant fails to have a frequency of resting CD4+ T cell infection to be  $\geq 0.3$  infected cells per million as determined by QVOA assay at the baseline leukapheresis in Step 1, study participation is terminated. The SID for this participant will be retired and will not be used again. These participants will be replaced in the study.

**7.4.2. Inability to manufacture HXTC therapy or failure to meet release criteria**

In the unlikely event that product or sufficient product is not successfully manufactured for participants, these participants would not proceed to Step 4 and would not undergo any further study procedures.

These participants may undergo a single repeat blood draw of 100mL to allow a second attempt at manufacturing product.

If the participant refuses to repeat the blood draw or the product cannot be manufactured after receipt of the 2nd 100 mL sample, the participant will be terminated from the study. The SID for this participant will be retired and will not be used again. These participants will be replaced in the study.

**7.4.3. Inability to meet the pre-dose lab guidelines for study progression based on clinical evaluations at Step 3, Visit 7 and at Step 4, Visit 13.**

If a participant's failure to move to Step 4 or Step 5 is due to an inability to meet one of the pre-dose safety laboratory assessments parameters, repeat the failed criteria one time only.

Participants failing to advance to Step 4, without receiving any combination treatment of VOR and HXTC, will terminate from the study. The SID for this participant will be retired and will not be used again. These participants will be replaced in the study.

Participants completing combination dosing in Step 4 and/or Step 5 who then fail to meet safety assessment requirements, will not receive further doses of VOR or HXTC. Participants will proceed to complete the early discontinuation visit per Step 6, Visit 23 (when clinically acceptable, per PI assessment) and continue to complete the longitudinal assessment at Visit 24.

## 7.5. Early Discontinuation Visit (Step 6, Visit 23)

Complete this visit any time a participant discontinues early from the study. This is the End of Study Intervention Visit and completed when participants complete study interventions, whether pre-maturely (as with an early discontinuation or upon successful completion of the study).

Perform the Early Discontinuation or End of Study Intervention Visit assessments and procedures per the SOE.

The Leukapheresis is completed on all participants who have completed all dosing visits. If a participant terminates early, completion of the leukapheresis at Visit 23 will be determined by study PI or the study team.

Estimated Blood Volume: up to 65 mL

## 8. STUDY PROCEDURES/EVALUATIONS

### 8.1. Description of Evaluations

Evaluation of participants occur by physical examinations, medical history, clinical laboratory tests, research lab assay results, vital sign measurements, and adverse event evaluations. Safety assessments will include grading of the frequency and severity of adverse events associated with study treatment including, but not limited to, clinical laboratory values, physical examination and evaluations of infusion site reactions.

#### 8.1.1. Clinical Evaluations and Procedures

##### 8.1.1.1. Informed Consent

Prior to performing any study-related procedure or assessments, the study coordinator discusses the study with the potential participant and obtains signed informed consent. This communication will be documented. Labs/procedures completed during a routine clinical care appointment that are the same as the study screening labs and/or procedures and completed within the 14 days preceding the screening visit can be used to qualify the participant upon approval by the study PI or designee.

##### 8.1.1.2. Study Eligibility

Determination of study eligibility by the Inclusion and Exclusion criteria occurs at Screening and prior to enrollment at Step 1, Visit 2. Potential participants failing eligibility will be considered a screen failure. (Please reference section 7.4.).

8.1.1.3. Advancement Criteria

There is one time point when participants are required to meet Advancement Criteria to continue on study:

Step 1 to Step 3

The leukapheresis procedure performed at or after enrollment in Step 1, Visit 2 determines the criteria required to advance to Step 3. Failure to meet the criteria results in participant's termination from the study.

Advancement Criteria for Step 3

- Participants with frequency of resting CD4+ T cell infection of < 0.3 IUPM by QVOA will not progress to Step 3, as a further decrease from this low frequency of infection cannot be definitively measured given the QVOA assay threshold.

8.1.1.4. Pre-Dose Lab Assessments

There are two time points in the study when the participant completes Pre-Dose Safety Lab Assessments. The lab results obtained in these assessments must be within the study established parameters for the administration of VOR to occur. Labs that fall outside the parameters can be repeated one time only to qualify participants to proceed.

After repeat testing, any lab values that remain outside the guidelines but considered clinically non-significant and documented as such by the study PI (or designee), must be reviewed and approved by the protocol and/or safety committee prior to dosing/infusion visit.

The time points of Pre-Dose Lab Assessments are:

1. Step 3, Visit 6 (1st Series of VOR doses (10) and two HXTC infusions)
2. Step 4, Visit 13 (2nd Series of VOR doses (10) and three HXTC infusions)

8.1.1.5. Complete Medical Histories

Significant medical history should be obtained during the Screening visit. All concurrent medical conditions in the last 30 days and any significant medical conditions (e.g., hospitalizations, surgeries, prior medical history) should be collected. Medical history obtained at Screening will include demographic information (e.g., date of birth, gender, race, and ethnicity, etc.), participant's medical history, and HIV history.

8.1.1.6. Update Medical History at all clinical visits

Any reported signs and symptoms or new diagnoses occurring after the participant signs the study consent but prior to the administration of the first

study dose will be recorded in the medical history (pre-existing condition) unless reported event is related to a protocol-related procedure.

8.1.1.7. **Complete Physical Exams**

A complete physical examination (PE) is done at the following visits:

- Step 1, Visit 1 - Screening
- Step 3, Visit 6
- Step 4, Visit 13 (Study Week 6)
- Step 6, Visit 23 (Study Week 16)
- Early Discontinuation Visit (same as End of Study Intervention Visit in SOE - Step 6, Visit 23 (Study Week 16))

The PE will include a complete review of systems, vital signs, and weight. Measure Height at the Screening Visit only. The complete physical examination will include examination of skin, head, eyes, ears, nose, throat, lymph nodes, heart, chest, lungs, abdomen, extremities, psychological and neurologic systems.

8.1.1.8. **Directed or Targeted Physical Exams**

A targeted PE is done at all other visits where a complete PE is not performed, per the SOE. A directed physical examination includes vital signs and addresses any previously identified or new event that the participant experiences since the last study visit or any unresolved signs or symptoms previously experienced. This assessment includes updates to signs and symptoms, and clinical assessment of HIV disease.

8.1.1.9. **Vital Signs**

Temperature, respiration, pulse, blood pressure, and weight (without shoes) at each study visit. Complete vital sign measurements after 5 minutes in the sitting position. Repeat vital signs may also be captured as necessary to elucidate the course of any untoward event or AE.

8.1.1.10. **Height** – required at study screening visit only without shoes.

8.1.1.11. **ART History**

May consist of a combination of participant report and clinical records where available. During the study, all modifications to the participant's ART regimen, including any ARV interruptions, dose modifications, formulations modifications, starts, and permanent discontinuations since the last study visit or at the study visit must be recorded.

8.1.1.12. **ART Adherence**

ART adherence will be reviewed at every visit. Any missed doses while on study should be discussed with Study PI (or designee). Continuance on study will be contingent on adherence.

8.1.1.13. **Concomitant Medication History**

Include all current medications and any PRN medications used within the past 30 days.

- All medication taken within 30 days of study screening.
- After study entry, record only new and discontinued over-the-counter, herbal, dietary and vitamin supplements, and prescription medications.
- Document all doses of VOR and HXTC therapy and permanent discontinuation.

8.1.1.14. **Signs, Symptoms, and Diagnosis of Illnesses and Diseases**

At screening, all signs and symptoms, regardless of grade, that occurred within the 30 days before entry must be recorded. After study entry, record any new diagnosis or illnesses that develop.

After study entry, grade  $\geq 3$  signs and symptoms must be recorded. Record only signs and symptoms that are related to VOR or HXTC therapy and all signs and symptoms that lead to a change in treatment, regardless of grade.

8.1.1.15. **Blood collection**

Please reference SOE in Appendix A

8.1.1.16. **Urine Collection**

Please reference SOE in Appendix A

8.1.1.17. **Assessment of adverse events**

Please reference protocol section 9.1

8.1.1.18. **Leukapheresis**

Participants will undergo two Leukapheresis procedures. The baseline leukapheresis will be completed at or after Visit 2. Participants will advance to Step 3 based on an IUPM measurement  $\geq 0.3$ . The 2nd leukapheresis will take place at the End of Study Intervention visit in Step 6, Visit 23.

All protocol required leukapheresis products will be transported on the day of collection to the [name] Laboratory on the UNC campus.

All leukapheresis procedures will occur at the UNC Apheresis Lab located in the UNC Blood Bank or at a local contracted blood collection center.

Note: Refer to the UNC Apheresis SOP and Study Specific Lab Manual for procedures specific to this study.

If participants experience a Grade 3 or higher toxicity in the screening leukapheresis, they will be discontinued from study, as completing the leukapheresis procedures is a requirement of the study screening process. Participants who experience a Grade 3 or higher toxicity related to any additional leukapheresis will be evaluated on a case by case basis to understand the cause of the Grade 3 event. If the clinical situations (i.e., vasovagal response) that lead to the discontinuation of the leukapheresis procedure is determined by the study PI in collaboration with the Apheresis Medical Director to be situational and poses no apparent harm to the participant, the leukapheresis procedure may be repeated. However, if determined by the study PI, Apheresis Medical Director, and/or the Medical Monitor that repeated leukapheresis would be harmful to the participant, then he/she will be terminated from the study.

The only exception to this discontinuation policy includes elevations in blood pressure (BP). Transiently elevated BPs to Grades 2 and 3 are frequently observed during this procedure, secondary to the BP cuff placement and nervousness of the participant. Elevated BP observed during the leukapheresis procedure will be monitored via Apheresis Lab policies. These will be noted and documented but will not be used to discontinue study participation.

- 8.1.1.19. **Pre-HXTC Infusion Medications** (cetirizine and acetaminophen) and other Medications for Administration in the Advent of a Hypersensitivity or Anaphylactic Reaction
  - Licensed study staff will administer cetirizine (PO) and the acetaminophen (PO).
  - Administration of medications for treatment of adverse reactions to the HXTC will follow hospital policy and the UNC HIV Cure Center SOP entitled Cellular Product Infusion Guidelines and Emergency Management Plan.

- 8.1.1.20. **HXTC Infusion**  
The HXTC will be administered by staff competent in cellular product infusion; the study PI (or designee) or a licensed physician assistant (PA)/nurse practitioner (NP) or RN. A research assistant (RA) may obtain and record vital signs and provide other participant care necessary during the HXTC infusion.

- 8.1.1.21. **Product Infusion Reaction Evaluations**

Participants will be monitored for up to 1 hour following treatment while the participant remains in the clinic. Participants will be instructed to contact study staff about any reactions that occur after receipt of the HXTC therapy. The study staff will contact the participants via telephone or their preferred way of communication approximately 2 to 3 days after the study product administration to inquire about reactions or any potential TEAEs. Infusion reactions will be graded according to the DAIDS toxicity grading table.

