## **9.1. Toxicity**

Only toxicities considered related to HXTC and/or VOR will be managed directly by this protocol.

Participants will be monitored closely for adverse effects. Toxicities will be characterized in terms including duration, intensity, and time to onset. Safety endpoints will include all adverse experiences, in addition to laboratory safety assessments and vital signs.

For this study, the hemoglobin will be graded using version 2.1 [July 2017] of the DAIDS Table for Grading the Severity of Adult and Pediatric Adverse Events where a hemoglobin <11 mg/dl for men and <10.5 for women will be considered a Grade 1 toxicity.

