### 9.2. Toxicity Management

#### 9.2.1. Adverse Events

Reports of AEs will be elicited by verbally questioning the participant at all visits. The study coordinator will also telephone the participant approximately 2 to 3 days after the HXTC study product administration to inquire about any potential treatment emergent adverse events (TEAE). The participant will be instructed to contact the study coordinator or investigator if such events occur at any point during the study.

Any events spontaneously reported by the participant or observed by the study team will be recorded.

If an AE occurs, the study coordinator, in collaboration with the PI or designee, will evaluate the severity and seriousness of the AE and the relationship to the study product, and will document the findings. Appropriate countermeasures, including medical intervention or procedures, must be instituted if indicated clinically.

AEs occurring at the HXTC administration site should be reported and analyzed in accordance with standard practices for clinical testing of novel therapeutic candidates.

All reactions will be graded according to the Division of AIDS (DAIDS) Table for Grading the Severity of Adult and Pediatric Adverse Events, Version 2.1 [July 2017], which is available on the DAIDS RSC website: <http://rsc.techres.com/safetyandpharmacovigilance/>.

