#### 9.2.3. Adverse Event Reporting Period

The AE reporting period for each participant begins when the participant signs the consent and lasts through the 30 days following the EOS visit in Step 6, Visit 24. During Step 1 and Step 3 (prior to study product administration), any AE that occurs will be collected as concurrent medical history (pre-existing condition) and not as an AE, unless it is due to a protocol-related procedure (e.g., leukapheresis or large blood collection for HXTC manufacturing).

AEs leading to discontinuation, AEs of  $\geq$  Grade 3 severity, related adverse events, and lab abnormalities as well as safety concerns will be recorded in the database as well as communicated in a timely manner to the UNC IRB, Children's National Health System IRB, NHLBI, FDA, and Merck per the reporting requirements of each regulatory entity.

The Sponsor of this study is UNC-CH. The principal investigator ([name]) at UNC-CH will be responsible for reporting to all the regulatory bodies and funding sources listed above.

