### **10.2. Outcome Measures**

#### **10.2.1. Primary Endpoints**

##### **10.2.1.1. Safety**

Occurrence of at least one  $\geq$  Grade 3 adverse event including signs/symptoms, lab toxicities, and/or clinical events that is possibly or definitely related to VOR or HXTc any time from the first day of study treatment through Step 6, Visit 23.

Safety data will include local and systemic signs and symptoms, laboratory measures of safety/toxicity, and all adverse and serious adverse events. Safety data will be routinely collected throughout the duration of the study.

NOTE: The occurrence of a Grade 3 infusion reaction that is sustained for less than 48 hours will not be included as a primary safety endpoint.

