## **10.7. Analysis**

### **10.7.1. Primary Analysis**

For the safety endpoint, we will record and describe all study treatment-related adverse events through the end of study.

Ultimately, we aim to detect a significant depletion of the latent reservoir, by measuring the frequency of resting cell infection using the QVOA. We will analyze pre-VOR/HXT and post-VOR/HXT frequency of HIV infection per million resting CD4+T cells using a non-parametric 2-sided sign test (and the Wilcoxon signed rank test if no assay censoring) to determine whether or not a significant decrease of IUPM is observed. With 12 participants there is 80% power to reject H0 (change expected with ART alone) in favor of HA (greater change than expected with ART) if

the true probability of observing a decrease in IUPM in a participant after VOR/HXTC is 0.93.

In addition to summarizing the number and proportion of participants who show decrease in IUPM after VOR/HXTC, we will describe the magnitude of the changes in decrease in IUPM after VOR/HXTC via the median fold-change and corresponding 95% confidence interval. We will also summarize the proportion of participants with >6-fold decreases; this magnitude change is rarely seen in participants on stable ART [64]. We will therefore consider a >6 fold change from baseline to post VOR-HXTC treatment as significant on an individual participant basis. For n=12 participants, precision calculations are analogous to those for safety endpoints. In particular, if all 12 participants have a >6 fold change from baseline, then the exact 95% confidence interval (CI) for the probability of significant depletion of the latent reservoir would be [0.74, 1.00], i.e., one could confidently rule out depletion probabilities less than 74%. If 11 of 12 participants achieve significant depletion, the 95% CI would be [0.62, 1.00]. Other possible observed proportions and 95% CIs are given in Table 5.

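### The AE recording rules contradict each other and only treatment-related AEs are to be described, so an all-cause account of low-grade tolerability is not assured

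*Combined protocol and SAP*

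**What the plan says.** Three places narrow what is captured or reported.

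- Section 8.1.1.14 (signs, symptoms and diagnoses) requires Grade 3 or higher signs and symptoms to be recorded after entry, then adds: "Record only signs and symptoms that are related to VOR or HXTC therapy", together with those of any grade that change treatment. The same section takes in any new diagnosis or illness, with no grade or causality condition.
- Section 9.2.3 (AE reporting period) names AEs that lead to discontinuation and AEs of Grade 3 or higher, and continues: "related adverse events, and lab abnormalities as well as safety concerns will be recorded in the database". The same sentence covers communication to the IRBs, the funder, the FDA and the drug supplier.
- Section 10.7.1 (primary analysis) says of the safety endpoint: "we will record and describe all study treatment-related adverse events through the end of study".

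Four places are broad.

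- Section 9.1: "Safety endpoints will include all adverse experiences".
- Section 9.2.1: "Any events spontaneously reported by the participant or observed by the study team will be recorded".
- Section 9.2.4 has each AE charted with onset, severity and a five-level causality scale whose lowest levels are unrelated and unlikely.
- Section 10.2.1.1 says that the safety data include "laboratory measures of safety/toxicity, and all adverse and serious adverse events".

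Section 9.2.2 defines an AE without regard to causality, which fits the broad set.

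**The concern.** Section 3.2.1 names safety and tolerability of the combination as the primary outcome. The trial has one arm and no blinding, so relatedness is the site's opinion, with no control rate to test it against. If section 8.1.1.14 is the rule that staff follow, that opinion becomes the condition for a low-grade symptom entering the record at all.

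Low-grade events are where the protocol's own experience lies. Section 2.2.5 reports nothing above Grade 1 with intermittent VOR in people with HIV, apart from one Grade 2 fatigue. Section 2.3.1 reports mild, transient fever, aches, chills and rigors after HIV-specific T cells. The dose rationale in section 2.1 says that all AEs under Version 2 were Grade 1 at most and attributed to apheresis. It cites that experience when proposing to raise the infusion from 2 x 10^7 to as much as 1 x 10^8 cells/m2, a factor of 5. AEs attributed to something other than VOR or HXTC were thus part of the safety account on which the increase was based. The description planned in section 10.7.1 would leave such events out.

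Causality is also hard to settle at first occurrence. Section 9.2.4 links it to improvement on stopping and return on re-exposure. With 20 VOR doses and 5 infusions, recurrence is useful evidence, but only if the first episode was written down. The monthly causality review in section 10.5 works on reported events.

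**Working it through.** **1. The plan's own safety figures, and whether this point touches them.** Inputs: n = 12 (section 10.3) and the one-sided confidence levels of 95% and 80% (section 10.4). Exact binomial limits:

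- 0 of 12, upper limit = 1 - a^(1/12). Two-sided 95%: 1 - 0.025^(1/12) = 0.265. One-sided 95%: 1 - 0.05^(1/12) = 0.221. One-sided 80%: 1 - 0.20^(1/12) = 0.126.
- 1 of 12, from beta quantiles (lower limit from Beta(1, 12), upper from Beta(2, 11)). Two-sided 95%: 0.002 to 0.385. One-sided 95%: 0.339. One-sided 80%: 0.230.

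Section 10.3 prints [0.00, 0.26] and [0.00, 0.38]. Section 10.4 prints 22%, 13%, 34% and 23%. All agree. These figures concern Grade 3 or higher related events. Signs and symptoms of that grade must be recorded under section 8.1.1.14, and AEs of that grade are on the database list in section 9.2.3. Changing the low-grade recording rule alters none of them.

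**2. Where each kind of post-dosing event goes.**

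| Event | 8.1.1.14 | Database list, 9.2.3 | Described, 10.7.1 | Within the broad sections |
|---|---|---|---|---|
| Sign or symptom, Grade 3+, any attribution | Recorded | Named | If related | Yes |
| Sign or symptom, Grade 1-2, related | Recorded | Named | Yes | Yes |
| Sign or symptom, Grade 1-2, unrelated, changes treatment | Recorded | Named if it leads to discontinuation | No | Yes |
| New diagnosis or illness, any grade | Recorded | Named if Grade 3+, related or leading to discontinuation | If related | Yes |
| Sign or symptom, Grade 1-2, unrelated, no treatment change | Not recorded | Not named, unless treated as a safety concern | No | Yes |

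The last row is the conflict in recording. Sections 9.2.1 and 9.2.4 would have the event recorded and charted, and sections 9.1 and 10.2.1.1 count it as safety data, but section 8.1.1.14 says not to record it. Staff are not able to follow both.

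**3. The analysis gap.** The column for section 10.7.1 shows a second gap that does not depend on which recording rule prevails. Even with complete charts and a complete database, the plan describes related AEs only. No table of AEs regardless of attribution is specified.

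**The case against.** The best defence is that section 8.1.1.14 governs only a signs-and-symptoms form, while section 9 governs AEs. Section 8.1.1.17 sends AE assessment to section 9.1, section 9.2.1 has no grade or causality filter, and the unrelated and unlikely levels in section 9.2.4 would have no purpose if such events were never charted. Section 9.2.3 does not say that its list is exclusive, and it contains the open category of safety concerns. The Version 2 account shows that low-grade AEs not attributed to study treatment were in fact captured, though under an earlier version and as procedure-related events. Related generally includes possibly related (sections 9, 9.1.1 and 10.5), which narrows the exposed group. Section 12.3.3 requires procedures covering serious and non-serious AEs and defers to a separate safety monitoring plan, not available here, that may settle database entry.

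Much of this stands. A reader might infer that an all-cause table would be impossible, or that no low-grade event judged unrelated would survive anywhere. The documents do not support that: there are two competing recording rules, the narrower one is not shown to prevail, and source charts could allow partial recovery. A reader might also infer that the primary safety result is biased by the recording rule. That is not supported either, because the endpoint in section 10.2.1.1 and the suspension rule in section 10.5 both concern related events of Grade 3 or higher.

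What the defence does not remove is the instruction in section 8.1.1.14, which on its face conflicts with section 9.2.1, or the restriction of section 10.7.1 to related events. A chart entry is also not a database entry.

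**Conclusion.** The point holds as an inconsistency in data capture together with a gap in the analysis. The exposed data are Grade 1-2 signs and symptoms judged unrelated that change no treatment. They may not reach the database, and no all-cause AE summary is planned for them or for other unrelated AEs. An all-cause tolerability table and later re-attribution are therefore not assured.

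The number of events concerned is unknown: the documents give no rate of low-grade symptoms judged unrelated, so no numerical effect is claimed. The primary endpoint, its confidence limits and the suspension rule stay as they are, although attribution of recorded Grade 3 or higher events remains an unblinded judgement.

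The conclusion assumes that the separate safety monitoring plan does not already require database entry of all AEs. If it does, the recording conflict is mainly one of wording, and the gap in section 10.7.1 remains. The change is worth making because tolerability is part of the primary outcome and the remedy is cheap.

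**What to change.** - Reconcile sections 8.1.1.14 and 9.2.3 with sections 9.1, 9.2.1, 9.2.4 and 10.2.1.1, so that AEs of any grade and any attribution are entered in the database from the first VOR dose to the end of the AE reporting period (30 days after Visit 24, section 9.2.3). Keep the existing capture of procedure-related AEs before dosing.
- In section 9.2.3, separate the list for prompt communication to outside bodies from the rule for database entry.
- Amend section 10.7.1 to tabulate the number of participants with AEs by maximum grade, first regardless of attribution and then restricted to related events.
- Leave the Grade 3 or higher related endpoint and its precision statements unchanged.

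The cost is modest extra CRF entry for 12 participants and one extra table. Section 9.2.1 already has AEs elicited at all visits and by telephone after each infusion, so no new contact with participants is needed.
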